9.3 Pregnancy and Lactation Reporting

If a pregnancy occurs in a female subject, or female partner of a male subject, while the subject is taking talimogene laherparepvec, report the pregnancy to Amgen as specified below.

In addition to reporting any pregnancies occurring during the talimogene laherparepvec treatment, investigators should monitor for pregnancies that occur after the last dose of talimogene laherparepvec through 3 months after the last dose of talimogene laherparepvec.

The pregnancy should be reported to Amgen Global Patient Safety within 24 hours of the investigator’s knowledge of the event of a pregnancy. Report a pregnancy on the Pregnancy Notification Worksheet ([Appendix C](#)).

If a lactation case occurs while the female subject is taking protocol-required therapies report the lactation case to Amgen as specified below.

In addition to reporting a lactation case during the talimogene laherparepvec treatment, investigators should monitor for lactation cases that occur after the last dose of talimogene laherparepvec through 3 months after the last dose of talimogene laherparepvec.

Any lactation case should be reported to Amgen Global Patient Safety within 24 hours of the investigator's knowledge of event. Report a lactation case on the Lactation Notification Worksheet ([Appendix C](#)).

9.4 Reporting of Exposure to Talimogene Laherparepvec

If a household member, caregiver, or healthcare provider who has had close contact with a subject treated with talimogene laherparepvec on this study is suspected to have been exposed to talimogene laherparepvec (eg, have or who have had signs or symptoms suspected to be herpetic in origin or who have been accidentally exposed to talimogene laherparepvec), while the subject is taking talimogene laherparepvec, report the exposure to Amgen as specified below. In addition to reporting an unintended exposure case during the study treatment, investigators should monitor for potential exposure cases that occur after the last dose of talimogene laherparepvec through 30 (+15) days after the last dose of talimogene laherparepvec.

Any potential or known unintended exposure should be reported to Amgen within 24 hours of the investigator's knowledge of the event of exposure. Amgen will seek to follow up with the exposed individual, if necessary, to collect more information about the exposed individual contact with clinical trial subject, signs and/or symptoms related to the exposure, medical history, and/or outcome of the exposure. If the exposed individual is reporting sign or symptoms suspected to be related to talimogene laherparepvec exposure, the exposed individual may be asked to have a swab taken to evaluate for the presence of talimogene laherparepvec in the lesion.

10. STATISTICAL CONSIDERATIONS

10.1 Study Endpoints, Analysis Sets, and Covariates

10.1.1 Study Endpoints

10.1.1.1 Primary Endpoint

- Recurrence-free Survival (RFS): RFS is defined as time from randomization to the date of the first of local, regional, or distant recurrence of melanoma or death due to any cause.

10.1.1.2 Secondary Endpoint

Efficacy Endpoints:

- **1-year**, 2-year, 3-year, 5-year RFS: The Kaplan-Meier (K-M) estimate of RFS rate at **1-year**, 2 years, 3 years and 5 years
- Rate of histopathology tumor-free margin (R0) surgical resection
- Rate of pathological complete response (pCR)
- Local recurrence-free survival (LRFS): Time from randomization to the date of the first of local disease recurrence or death due to any cause. Local recurrence is defined as histologically or cytologically confirmed reappearance of melanoma in the in the area of up to 2 cm from the scar from the surgical excision or at the edge of the skin graft if that was used for closure
- Regional recurrence-free survival (RRFS): Time from randomization to the date of the first of regional disease recurrence or death due to any cause. Regional recurrence excludes local recurrence and is defined as histologically, cytologically, or radiographically confirmed reappearance of melanoma in the regional lymph node basin. New in-transit melanoma metastases in the regional lymphatic drainage will be reported as regional recurrence. Histological or cytological confirmation of new in-transit metastases is recommended but is not required.
- Distant metastases free survival (DMFS): Time from randomization to the date of the first of distant metastases or death due to any cause. Distant metastases exclude local and regional recurrence and will include distant cutaneous/subcutaneous metastases, distant nodal metastases, or visceral, central nervous system, brain, or bone metastases.
- Overall survival (OS): Time from randomization to death due to any cause
- **1-year**, 2-year, 3-year and 5-year survival: The Kaplan-Meier (K-M) estimate of the survival rate at **1-year**, 2 years, 3 years and 5 years
- Overall tumor response and tumor response in injected and uninjected lesions (Arm 1 only): The tumor response is evaluated up to the surgical resection. The overall tumor response is per the modified WHO ([Appendix D](#)). For tumor response in injected and uninjected lesions both subject-level and lesion-level response will be assessed. The subject-level injected and uninjected responses will be based on the tumor burden of only injected index lesions including injected new measurable lesions, or the tumor burden of only uninjected index lesions including uninjected new measurable lesions, respectively. The lesion-level response will evaluate the change of the area of each individual lesion. For the tumor response based on the tumor burden of a subset of lesions (injected/uninjected lesions) or individual lesions, a response is achieved if the percentage of tumor burden reduction from baseline is at least 50%. The related endpoints, such as time to response, may also be evaluated if appropriate.

Safety Endpoints:

- Subject incidence of treatment-emergent and treatment-related adverse events

10.1.1.3 Exploratory Endpoints

- Correlation between baseline intratumoral CD8+ cell density and clinical outcomes
- Correlation between changes in an intratumoral CD8+ cell density during talimogene laherparepvec treatment and clinical outcomes
- Correlation between the changes in the population of tumor-specific cytotoxic T-cells during treatment and clinical outcomes
- Assessment of blood and tumor for potential biomarkers which correlate with or predict clinical outcomes to talimogene laherparepvec

10.1.2 Analysis Sets

Intent to Treat Analysis Set

The primary analysis of all efficacy endpoints of the study will be conducted on the intent to treat analysis set defined as all randomized subjects who were randomized to either treatment arm. All subjects will be analyzed according to their treatment randomization.

Safety Analysis Set

The safety analysis set will include all subjects who received talimogene laherparepvec or surgical resection of melanoma tumor lesion(s). The safety analyses will be performed by treatment received.

Efficacy Analysis Set

The efficacy analysis set will include all subjects in Arm 1 who received at least one dose of talimogene laherparepvec and surgical resection of melanoma tumor lesion(s) and all the subjects in Arm 2 who received surgical resection of melanoma tumor lesion(s). In addition, all subjects in the efficacy analysis set must have achieved histopathologic tumor-free margin (R0) status after surgery and should not have any important protocol deviations which may affect the efficacy endpoints. The efficacy analysis set may be used for sensitivity analysis of efficacy endpoints if needed.

10.1.3 Covariates and Subgroups

Besides the stratification factors, the following covariates may be used to examine efficacy and safety in subgroups or in multivariate analyses:

- Region, if applicable (USA or non-USA)
- Age at baseline: < 50, ≥ 50; < 65, ≥ 65; < 75, ≥ 75 years
- Number of measurable tumors at baseline
- Presence of uninjected tumors at baseline and during the treatment: yes vs no
- The sum of the products of the two largest perpendicular diameters of baseline measurable lesions

- Baseline absolute lymphocyte count: ≤ 1000 vs > 1000
- Recurrent disease ≥ 1 year from primary diagnosis vs recurrent disease < 1 year from primary diagnosis vs no prior melanoma

10.2 Sample Size Considerations

All analyses will be descriptive with no formal hypothesis testing. The primary objective of the study is to estimate the treatment effect, as measured by the hazard ratio of RFS, of talimogene laherparepvec neoadjuvant therapy followed by surgery (Arm 1) compared to surgery alone (Arm 2) in subjects with resectable, stage IIIB to IVM1a melanoma.

Approximately 150 subjects will be randomized 1:1 to receive Arm 1 vs Arm 2 stratified by: (i) disease stage (IIIB nodal vs IIIB in-transit vs IIIC nodal vs IIIC in-transit with nodal vs IVM1a), and (ii) planned adjuvant therapy (adjuvant systemic therapy [eg, INF α , ipilimumab] with or without radiotherapy vs radiotherapy without adjuvant systemic therapy vs none).

Primary efficacy analysis of RFS will be based on the Intent to Treat Analysis Set. An overall between-group difference in RFS will be evaluated with a log-rank test and corresponding proportional hazard model without stratification. The Kaplan-Meier (KM) method will be used to estimate **1-year**, 2-year, 3-year, 5-year, and overall RFS. Subjects who are not confirmed to be disease-free post-surgery (ie, who do not have an R0 surgical outcome) or who withdraw prior to surgery will be considered a failure a day after randomization for RFS.

The primary analysis for the primary endpoint will occur at the later time of either the occurrence of approximately 64 events (local, regional, or distant recurrence of melanoma or death) or approximately 2 years after the end of randomization. An 80% CI will be estimated for the hazard ratio of RFS. In addition, an 80% CI will also be estimated for the between-arm difference (Arm 2 – Arm 1) in 2-year RFS, ie, Δ 2-year RFS. It is assumed that: (i) RFS is exponential over the first 2 years, (ii) the 2-year RFS for Arm 1 is about 0.60 (Eggermont et al, 2008), and that there will be a 10% exponential probability of drop-out by the primary analysis. Simulations were used to evaluate the following parameters assuming possible true Δ 2-year RFS values of 0.05, 0.10, and 0.15: (i) the average Δ 2-year RFS 80% CI and its width, (ii) the probability that the Δ 2-year RFS 80% CI is above 0, and (iii) the average number of events at the primary analysis. The possible true Δ 2-year RFS values were translated to a RFS hazard ratio (HR) (Arm 2 relative to Arm 1) and the HR 80% CI and the probability of it being

< 1 were calculated based on the simulated average number of events. The average width of the Δ 2-year RFS 80% CI was 0.20 (Table 5).

Table 5. Study Design Characteristics

2-year RFS			RFS HR	Ave. Δ 80% CI			Prob. Δ 80% CI > 0	Ave. HR 80% CI		Prob. HR 80% CI < 1	Ave. Events
Arm 1	Arm 2	Δ		LL	UL	Width		LL	UL		
0.70		0.100	0.70	0.00	0.20	0.20	0.51	0.51	0.96	0.56	64
0.725	0.60	0.125	0.63	0.02	0.22	0.20	0.62	0.45	0.87	0.71	62
0.750		0.150	0.56	0.05	0.25	0.20	0.74	0.40	0.78	0.83	60

RFS, Recurrence-free Survival; HR, Hazard Ratio; CI, Confidence Interval; LL, Lower Limit; UL, Upper Limit; Ave, Average; Prob., Probability; Δ = Arm 2 – Arm 1 2-year RFS

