3.5 Estimated Study Duration

3.5.1 Study Duration for Subjects

The duration for the study will be approximately 7 years. The duration of screening for each subject will be approximately 28 days. The subject accrual period is planned for approximately 18 months. The duration of treatment will vary by treatment arm.

Subjects randomized to Arm 1 of the study will be treated with talimogene laherparepvec for approximately 12 weeks then followed by surgical resection of melanoma lesion(s) any time from week 13 to 18. Subjects randomized to Arm 2 of the study will undergo immediate surgical resection of melanoma lesion(s) any time from week 1 to 6. Subjects will be followed for safety approximately 30 (+15) days after surgery and for disease recurrence (local, regional, or distant), subsequent anticancer therapy for melanoma, adverse events thought to be potentially related to talimogene laherparepvec, and survival every 3 months (± 30 days) for first 3 years after the end of the safety follow-up

period and then every 6 months (± 30 days) until death, subject withdraws full consent, or up to 5 years after the last subject is randomized, which is first.

The end of study for each subject is defined as the date the subject withdraws full consent from the study, completes the long-term survival follow-up, or death.

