### 3.2 Sample Size

All analyses will be descriptive with no formal hypothesis testing. The primary objective of the study is to estimate the treatment effect, as measured by the hazard ratio of RFS, of talimogene laherparepvec neoadjuvant therapy followed by surgery (Arm 1) compared to surgery alone (Arm 2) in subjects with resectable, stage IIIB to IVM1a melanoma. Approximately 150 subjects will be randomized 1:1 to receive Arm 1 vs Arm 2 stratified by: (i) disease stage (IIIB nodal vs IIIB in-transit vs IIIC nodal vs IIIC in-transit with nodal vs IVM1a), and (ii) planned adjuvant therapy (adjuvant systemic therapy [eg, INF $\alpha$ , ipilimumab] with or without radiotherapy vs radiotherapy without adjuvant systemic therapy vs none). Primary efficacy analysis of RFS will be based on the Intent to Treat Analysis Set. An overall between-group difference in RFS will be evaluated with a log-rank test and corresponding proportional hazards model without stratification. The Kaplan-Meier (KM) method will be used to estimate 1-year, 2-year, 3-year, 5-year, and overall RFS. Subjects who are not confirmed to be disease-free post-surgery (i.e., who do not have an R0 surgical outcome) or who withdraw prior to surgery will be considered a failure at randomization for RFS, RRFS, LRFS and DMFS. The primary analysis for the primary endpoint will occur at the later time of either the occurrence of approximately 64 events (local, regional, or distant recurrence of melanoma or death) or approximately 2 years after the end of randomization. An 80% CI will be estimated for the hazard ratio of RFS. In addition, an 80% CI will also be estimated for the between-arm difference (Arm 1 – Arm 2) in 2-year RFS, i.e.,  $\Delta$  2-year RFS. It is assumed that: (i) RFS is exponential over the first 2 years, (ii) the 2-year RFS for Arm 2 is about 0.60 (Eggermont et al, 2008), and that there will be a 10% exponential probability of drop-out by the primary analysis. Simulations were performed for various scenarios from 0.05 to 0.15 to evaluate the following parameters assuming possible true  $\Delta$  2-year RFS values of 0.10, 0.125, and 0.15: (i) the average  $\Delta$  2-year RFS 80% CI and its width, (ii) the probability that the  $\Delta$  2-year RFS 80% CI is above 0, and (iii) the average number of events at the

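### Protocol Table 5 and SAP Table 1 print 62 and 60 average events at the primary RFS analysis, which the later-of-64-events rule does not allow; the effect on precision is small, the effect on timing larger but assumption-dependent

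*Protocol*

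**What the plan says.** Protocol 10.2 sets the timing of the RFS analysis: "The primary analysis for the primary endpoint will occur at the later time of either the occurrence of approximately 64 events" or about 2 years after randomization closes. Protocol 10.4.3 and SAP 8.2 repeat the rule, and SAP 3.2 has it as well ("will occur at the later time of either the occurrence of approximately 64 events").

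The same sections say that simulation gave the mean event count at this primary analysis, and that the hazard ratio interval and the chance of its lying below 1 were computed from that mean. Protocol Table 5 and SAP Table 1 print the results:

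| 2-year RFS, Arm 1 vs Arm 2 | HR | HR 80% CI | Prob. CI below 1 | Average events |
|---|---|---|---|---|
| 0.70 vs 0.60 | 0.70 | 0.51 to 0.96 | 0.56 | 64 |
| 0.725 vs 0.60 | 0.63 | 0.45 to 0.87 | 0.71 | 62 |
| 0.75 vs 0.60 | 0.56 | 0.40 to 0.78 | 0.83 | 60 |

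Protocol 10.2 describes the simulations as "assuming possible true Δ 2-year RFS values of 0.05, 0.10, and 0.15", which is not the set of rows shown. SAP 3.2 says scenarios between 0.05 and 0.15 were run and lists the three differences that its table displays.

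**The concern.** Waiting for the later of two conditions puts a floor under the event count. A trial with 64 events by the 2-year date is analyzed with 64 or more; a trial with fewer waits until it has them. The mean over trials must be at least about 64, in every row. Counts of 62 and 60 cannot come from that rule, and a count that falls as the effect grows is what a calendar cut produces.

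Two things could be at stake. First, the hazard ratio intervals and probabilities are built on these counts, so they could misstate what the trial will deliver. Second, a reader planning around the 2-year date is not told how often the event condition will push the analysis later. The check below sizes both.

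**Working it through.** **Inputs from the documents**

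- Size: "Approximately 150 subjects will be randomized 1:1 to receive Arm 1 vs Arm 2 stratified by" the two randomization factors, so 75 per arm.
- Control rate: "the 2-year RFS for Arm 2 is about 0.60" (SAP 3.2, agreeing with both tables; the protocol 10.2 text attaches 0.60 to Arm 1, a separate labelling slip).
- Arm 1 rates: 0.70, 0.725, 0.75 (tables).
- RFS: exponential over the first 2 years. Drop-out: 10%, exponential, by the primary analysis (both in protocol 10.2).
- Interval: "An 80% CI will be estimated for the hazard ratio of RFS", so z = 1.2816.
- Accrual: "The subject accrual period is planned for approximately 18 months" (protocol 3.5.1).

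**Assumptions of mine.** Accrual is uniform, the simulation used the 18 months of section 3.5.1, the 10% drop-out is reached at month 42 (18 + 24), and RFS stays exponential after 2 years. Section 10.2 states none of these.

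**Step 1: reproduce the printed counts with a fixed cut.** For each arm λ = −ln(2-year RFS)/2 per year. Drop-out hazard δ = −ln(0.90)/3.5 = 0.0301, and m = λ + δ. At a cut 2 years after the last randomization, follow-up is uniform on 2 to 3.5 years, so

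expected events = 75 × (λ/m) × (1 − E), with E = [exp(−2m) − exp(−3.5m)]/(1.5m).

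| Arm | λ | m | E | Events |
|---|---|---|---|---|
| 0.60 | 0.2554 | 0.2855 | 0.4595 | 36.26 |
| 0.70 | 0.1783 | 0.2084 | 0.5660 | 27.85 |
| 0.725 | 0.1608 | 0.1909 | 0.5936 | 25.67 |
| 0.75 | 0.1438 | 0.1739 | 0.6216 | 23.47 |

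Adding the control arm gives 64.1, 61.9 and 59.7, that is, the printed 64, 62 and 60.

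**Step 2: how specific is the match?** The same formula with other inputs gives, for the three rows:

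- 12-month accrual: 60.1, 58.0, 55.9 (no match);
- 18-month accrual, no drop-out: 66.5, 64.3, 62.0 (no match);
- 18-month accrual, 10% drop-out by month 24: 62.4, 60.2, 58.1 (no match);
- 21-month accrual, 10% drop-out by month 24: 64.1, 62.0, 59.8 (match).

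So the inputs are not uniquely identified. Both matching sets use a fixed cut.

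**Step 3: apply the stated rule.** Simulated trials with the Step 1 inputs, counting events at the later of month 42 and the 64th event, average about 66.4, 65.4 and 64.8.

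**Step 4: effect on the hazard ratio columns.** HR = ln(Arm 1 rate)/ln(0.60) = 0.698, 0.630, 0.563. Standard error = 2/√events. Interval = HR × exp(±1.2816 × SE). Probability = Φ(−ln HR/SE − 1.2816).

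| Row | Events | HR 80% CI | Prob. |
|---|---|---|---|
| 1, as printed | 64 | 0.507 to 0.962 | 0.562 |
| 1, later-of | 66.4 | 0.510 to 0.956 | 0.572 |
| 2, as printed | 62 | 0.455 to 0.872 | 0.706 |
| 2, later-of | 65.4 | 0.459 to 0.864 | 0.722 |
| 3, as printed | 60 | 0.405 to 0.784 | 0.827 |
| 3, later-of | 64.8 | 0.410 to 0.774 | 0.848 |

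The printed counts recover the printed intervals and probabilities, which confirms the method. Under the later-of rule no limit moves by more than about 0.01 and no probability by more than about 0.02.

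**Step 5: the 2-year difference columns.** At the earliest permitted cut every subject already has 2 years of potential follow-up. Waiting longer adds nothing to the estimate at 2 years, so the limits, the 0.20 width and the probabilities stay.

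**Step 6: timing.** With 18-month accrual, and the drop-out spread over 42 or over 24 months:

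| Row | Trials below 64 events at the 2-year date | Mean delay over all trials (months) |
|---|---|---|
| 1 | 46% to 57% | 1.6 to 2.6 |
| 2 | 60% to 72% | 2.7 to 3.9 |
| 3 | 74% to 83% | 3.9 to 5.5 |

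The upper ends use the 24-month drop-out, which does not itself reproduce the table; they show sensitivity. Slower accrual shortens the wait: 24 months with drop-out by month 24 gives mean delays of 1.3, 2.2 and 3.6 months. A hazard that falls after year 2 lengthens it: halving it, purely as an illustration, with the Step 1 drop-out gives about 9, 12 and 16 months.

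**The case against.** The case for leaving the tables alone is a fair one. The trial is for estimation: "All analyses will be descriptive with no formal hypothesis testing". Its sample size is presented through the 0.20 width of the interval for the 2-year difference, which is untouched. The printed hazard ratio probabilities are slightly conservative. Both triggers are approximate, and 60 is only 6% below 64 (4/64). The later-of rule is stated openly in several places, and counts of 62 and 60 beside a 64-event trigger already hint that a larger effect may need a longer wait. The trigger also equals the first row's count, so the table may be the planning calculation from which 64 was chosen. Finally, the fixed cut is an inference; no section says what cut the simulation used.

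Most of this stands, and it limits the point to a correction of the table. It does not remove the mismatch: the column is described as the count at the primary analysis, and the rule for that analysis excludes 62 and 60.

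A reader might go further and infer that the hazard ratio intervals and probabilities are unusable. Step 4 does not support that. Nor do the documents support saying that the least favorable scenario, a difference of 0.05, was concealed: SAP 3.2 mentions that scenarios down to 0.05 were run and lists exactly the rows it tabulates. What remains is protocol wording that does not match its own table. Adding a 0.05 row, or a column of expected calendar time, is optional reporting.

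**Conclusion.** The point holds as a mislabelled design figure. That 62 and 60 lie below the floor follows from the text alone and needs no simulation. That the counts come from a cut at the 2-year date is an inference, well supported because such a cut reproduces all three rows, but dependent on unstated accrual and drop-out inputs.

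Its size for precision is small: about 66, 65 and 65 events in place of 64, 62 and 60; hazard ratio intervals of about 0.51 to 0.96, 0.46 to 0.86 and 0.41 to 0.77; probabilities of 0.57, 0.72 and 0.85.

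For timing it is larger. Under the assumptions of Step 6, the event condition rather than the date sets the analysis in roughly half of trials in the first row and in about three quarters or more in the third. The delay in months should be read as a range, since it rests on exponential RFS beyond the 2 years for which the protocol assumes it. Nothing here bears on the sample size, the trigger or the planned estimates.

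**What to change.** In protocol Table 5 and SAP Table 1, do one of the following:

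- re-run the event and hazard ratio columns under the later-of rule, and state the accrual pattern and the period over which the 10% drop-out applies; or
- keep the numbers and add a footnote that they are counts at a cut 2 years after randomization ends, and that the 64-event condition may set a later date (once the sponsor has confirmed that this was the cut used).

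In either case, change the scenario list in protocol 10.2 (0.05, 0.10, 0.15) to the rows shown (0.10, 0.125, 0.15), as SAP 3.2 already does.

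The cost is one short simulation or one footnote, plus a wording correction, carried into two documents.
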